Appendix 4. ADDITIONAL METHODOLOGY DETAILS

Details of Bayesian analysis of posterior distributions of the SDAI scores

Notation/Definitions

$i = 1, 2, \dots, n$; where n is the total number of patients

x_i^B = Baseline SDAI score for Patient i

x_i^W = Week W SDAI score for Patient i

$y_i = -(x_i^W - x_i^B)$; negative change from baseline SDAI at Week W for Patient i

$I_i^D = \begin{cases} 1, & \text{if Patient } i \text{ received Treatment D} \\ 0, & \text{otherwise.} \end{cases}$

A = Active treated group

P = Placebo treated group

Primary Model – Bayesian Analysis of Covariance

$$y_i = \mu_p^* I_i^P + (\mu_p^* + \Delta^*) I_i^A + \beta(x_i^B - \mu^B) + \varepsilon_i,$$

where $\varepsilon_i \sim N(0, \sigma_\varepsilon^2)$

Prior Models:

$\mu_p^* \sim N(13.7, \sigma^2 = 25)$

$\Delta^* \sim N(0, 10^3)$

$\beta \sim N(0, 10^3)$

$\sigma_\varepsilon^2 = \text{Noninformative inverse gamma } IG(0.001, 0.001)$

Note: μ_p^H is calculated based on commensurability between the historic and current study baseline patient profiles including both arms. The baseline profiles were based on baseline SDAI score prior ant-TNF exposure status. Geographic data was not used in the assessment of the prior distribution.

At least two alternative sensitivity prior models will be considered for μ_p^H , with one being a noninformative prior $N(0, 10^3)$. Also sensitivity models will be considered with ε_i modeled using t distribution with three degrees of freedom.

Data visualization techniques

Table shells of figures displaying the primary endpoint results (see below) will be provided in programming document.

- Distribution of treatment effect Δ^* .
- Display of change from baseline by treatment group based on Bayesian Analysis of Covariance.
- Display of change from baseline by treatment group based on Bayesian Analysis of Covariance vs baseline SDAI.

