9.2. Efficacy Analysis

9.2.1. Analysis of the Primary Endpoint

The primary efficacy analysis will be conducted on SDAI change from baseline at 8 weeks.

Analysis will include data on PF-06651600 and placebo arms.

Analysis details will be outlined in statistical analysis plan. The analysis will include: ANCOVA models adjusting for SDAI baseline value; Bayesian analysis of posterior distributions of the SDAI scores and placebo adjusted change from baseline; Advanced data visualization techniques for statistical result presentation.

The primary analysis will be conducted on intention-to-treat (ITT) population (randomized subjects with at least one post baseline value). Sensitivity analysis and handling of the missing values will be outlined in the SAP.

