9.4. Randomization

The indicator of prior exposure and inadequate response to anti-TNF α treatment will be used as a stratification variable for randomization. Randomization will be stratified to achieve equal proportion of anti-TNF α inadequate responders in all arms.

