6.1.2. Sensitivity/Robustness Analyses

There are 3 sets of analyses.

Set 1:

The sensitivity analysis will be based sensitivity prior models on the Bayesian analysis outlined in [Appendix 4](#).

Set 2:

- Missing data imputation
 - Observed
 - LOCF
- ANCOVA (see [Section 5.2.2](#))
 - Baseline SDAI as a covariate
 - Baseline SDAI and previous anti-TNF use as covariates

Set 3:

- Missing data imputation – none (Observed).
- MMRM (see [Section 5.2.2](#)) for analysis of change from baseline in SDAI at Weeks 1, 2, 4, 6, and 8.
 - Baseline SDAI as a covariate
 - Baseline SDAI and previous anti-TNF use as covariates

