9. APPENDICES

Appendix 1. SUMMARY OF EFFICACY ANALYSES

All efficacy analyses will be based on ITT set. Treatment groups will be PF-06651600 and placebo.

Primary Efficacy Endpoint	Statistical Method	Missing Data
Change from baseline in SDAI at Week 8	ANCOVA with baseline SDAI as a covariate	Observed
Change from baseline in SDAI at Week 8	ANCOVA with baseline SDAI as a covariate	LOCF
Change from baseline in SDAI at Week 8	ANCOVA with baseline SDAI and anti-TNF use as covariates	Observed
Change from baseline in SDAI at Week 8	ANCOVA with baseline SDAI and anti-TNF use as covariates	LOCF
Change from baseline in SDAI at Week 8	Bayesian analysis of posterior distributions of the SDAI scores and placebo adjusted change from baseline	-

Secondary Efficacy Endpoints	Statistical Method	Missing Data
SDAI remission and low disease activity at Weeks 4, 6, and 8	Normal approximation	Observed
SDAI remission and low disease activity at Weeks 4, 6, and 8	Normal approximation	NRI
DAS28-3 (ESR), DAS28-3 (CRP), DAS28 -4 (ESR), and DAS28-4 (CRP) remission and disease activity at Weeks 4, 6, and 8	Normal approximation	Observed
DAS28-3 (ESR), DAS28-3 (CRP), DAS28 -4 (ESR), and DAS28-4 (CRP) remission and disease activity at Weeks 4, 6, and 8	Normal approximation	NRI

Change from baseline in SDAI at Weeks 1, 2, 4, 6, and 8	MMRM	Observed
Change from baseline in DAS28 (eg, DAS28-3 (ESR), DAS28-3 (CRP), DAS28 -4 (ESR), and DAS28-4 (CRP)) at Weeks 1, 2, 4, 6, and 8	MMRM	Observed
Change from baseline in hsCRP at Weeks 1, 2, 4, 6, and 8	MMRM	Observed
Change from baseline in in the Tender/Painful and Swollen Joint Count (28) at Weeks 1, 2, 4, 6, and 8	MMRM	Observed
Change from baseline in PhGA of Arthritis at Weeks 1, 2, 4, 6, and 8	MMRM	Observed

Outcomes Research Endpoints	Statistical Method	Missing Data
-----------------------------	--------------------	--------------

Change from baseline in in PAAP VAS and PtGA of Arthritis VAS at Weeks 1, 2, 4, 6, and 8	MMRM	Observed
Change from baseline in in the HAQ-DI at Weeks 1, 2, 4, 6, and 8	MMRM	Observed

CCI

CCI

ACR20, ACR50, and ACR70 at Weeks 4, 6, and 8	CCI	
ACR20, ACR50, and ACR70 at Weeks 4, 6, and 8	CCI	

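### Randomisation is stratified on prior anti-TNF inadequate response, but neither the primary Bayesian model nor any listed Bayesian sensitivity model includes the stratum

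*SAP*

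**What the plan says.** Protocol 9.4 states that the indicator of prior exposure and inadequate response to anti-TNF treatment "will be used as a stratification variable for randomization", so that the arms have the same proportion of such subjects.

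SAP 6.1.1 makes the Bayesian analysis in Appendix 4 primary. Under "Primary Model – Bayesian Analysis of Covariance" the equation has four parts: a placebo mean, a treatment effect, a slope on centred baseline SDAI, and an error. There is no stratum term. This matches Protocol 9.2.1, which mentions "ANCOVA models adjusting for SDAI baseline value" and no other covariate.

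Appendix 4 lists two kinds of Bayesian sensitivity analysis. For the placebo mean, "At least two alternative sensitivity prior models will be considered", one of them noninformative. For the errors, there are models with the error "modeled using t distribution with three degrees of freedom". Neither kind changes the covariates.

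Anti-TNF status does appear elsewhere:

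- In deriving the placebo prior: "The baseline profiles were based on baseline SDAI score prior ant-TNF exposure status", using subjects from both arms.
- In the frequentist sensitivity analyses of SAP 6.1.2 (ANCOVA and MMRM), one version of each has "Baseline SDAI and previous anti-TNF use as covariates". Appendix 1 repeats the ANCOVA version: "ANCOVA with baseline SDAI and anti-TNF use as covariates".
- In the descriptive SDAI summaries of SAP 6.5.

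**The concern.** A factor worth stratifying on is normally expected to be prognostic, and an analysis should then respect it. Leaving it out has two consequences.

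1. **Strata balanced.** Stratified allocation removes the stratum's contribution to the variance of the treatment contrast. A model without the term still counts that contribution as residual variance, so the reported posterior SD exceeds the real uncertainty. On this account the interval is conservative.
2. **Strata unequal among analysed subjects**, for example after dropout. Part of the stratum difference is then attributed to treatment. The error can go in either direction, so it is not always conservative. The placebo data also cease to represent the stratum mix for which the N(13.7, 25) prior was built.

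The sponsor treats anti-TNF status as important enough to stratify on, to match historical data on and to include in the frequentist models. The analysis that carries the decision rule of SAP 5.1, Pr(effect > 0) above 90%, is the one that omits it.

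**Working it through.** **Inputs.** Protocol 9.1: 30 active and 20 placebo completers, SD 14 (variance 196), planned difference 13. Protocol 4.1, criterion 11: at most 50% anti-TNF-experienced. SAP Appendix 4: placebo-mean prior variance 25, effect prior variance 1000, IG(0.001, 0.001) for the residual variance. **Assumed, because the documents give none:** a stratum gap d of 0, 5 or 10 SDAI points remaining after baseline SDAI adjustment, with total SD held at 14, and stratum prevalence f of 50% or 30%.

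**The plan's own power figure.** The standard error is 14 × √(1/30 + 1/20) = 4.04, and 13/4.04 = 3.217. Power is Φ(3.217 − 1.960) = 89.6% two-sided at 5%, or Φ(3.217 − 1.645) = 94.2% one-sided. The stated value of over 90% is therefore reproduced to within rounding two-sided and met outright one-sided. For enrolment, 50/0.85 = 58.8, consistent with about 60.

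**Balanced strata.** With the stratum in the model the residual variance is v = 196 − f(1 − f)d². Treating v as known,

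posterior variance of the effect = 1 / {1/1000 + 1/[v/30 + 1/(20/v + 1/25)]}.

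Without the term, v = 196: 196/30 = 6.533; 1/(20/196 + 0.04) = 7.040; the sum is 13.574; the variance is 13.39 and the SD 3.659. With the term:

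| f | d | v | Posterior SD | Change |
|---|---|---|---|---|
| 50% | 0 | 196 | 3.659 | 0% |
| 50% | 5 | 189.75 | 3.610 | −1.4% |
| 50% | 10 | 171 | 3.454 | −5.6% |
| 30% | 5 | 190.75 | 3.618 | −1.1% |
| 30% | 10 | 175 | 3.488 | −4.7% |

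Simulation with the full Appendix 4 priors (40,000 trials per setting, true placebo mean 13.7, f = 50%, d = 10):

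| | Without term | With term |
|---|---|---|
| Empirical SD of the estimate | 3.14 | 3.20 |
| Mean posterior SD | 3.70 | 3.48 |
| Pr > 0.90 reached, effect 0 | 7.1% | 8.8% |
| Pr > 0.90 reached, effect 13 | 99.50% | 99.56% |

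So the term does not make the estimate more precise here. It brings the reported SD closer to the real one. Part of the remaining excess comes from the informative prior.

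**Unequal strata.** Suppose 15/30 active and 7/20 placebo subjects are in the stratum (22/50 = 44% overall) and stratum members improve by d points less.

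- The active mean moves by −(0.50 − 0.44)d = −0.06d and the placebo mean by +(0.44 − 0.35)d = +0.09d.
- The placebo data have weight (20/196)/(20/196 + 1/25) = 0.718 against the prior, and the effect prior shrinks the estimate by a factor of 0.987.
- Bias = −0.987 × (0.06 + 0.718 × 0.09)d = −0.123d, which is −0.6 points for d = 5 and −1.2 for d = 10.
- Simulation gives −0.60 and −1.25 without the term, and 0.01 and −0.05 with it.

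The opposite pattern, 13/30 against 12/20 with d = 8, inflates the effect. In 3,000 simulated trials with an approximate posterior the bias is +1.1 without the term and about 0 with it, and with no true effect the 90% rule is met in 13.2% against 8.5% of trials.

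**Cost if the stratum does not matter (d = 0).** The posterior SD is unchanged with balanced strata and rises from 3.69 to 3.72 (about 0.9%) in the 15/30 against 7/20 example.

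**The case against.** The strongest reply is that the plan already deals with the stratum. ANCOVA on observed and LOCF data, and MMRM, are specified with anti-TNF use as a covariate. A Bayesian ANCOVA with vague priors and a stratum term would give nearly the same answer as the adjusted ANCOVA. This largely stands, and it limits the gap to the combination of stratum and informative prior. It does not close the gap. If the frequentist and primary results differ, a reader cannot tell whether the prior or the covariate is responsible.

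The second reply is that the effect is small. A 10-point gap after baseline adjustment would be 77% of the planned treatment difference (10/13), and the 5.6% figure also needs prevalence at the cap. In the balanced case the term raises the no-effect success rate from 7.1% to 8.8%, so omission is protective there. All of this is correct.

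The third reply is that the imbalance examples are unusual. Assume 36/24 randomised with balanced strata, 30/20 completing, and dropout unrelated to stratum. A difference of 15 percentage points or more, in either direction, then has probability of about 1% to 2%. The typical (1 SD) difference is about 6 points, worth 0.06 × 5 = 0.3 to 0.06 × 10 = 0.6 SDAI points before shrinkage by the prior. This stands too. The examples show what happens if dropout depends on the stratum, and the documents do not suggest that it will. The shift in the placebo mix is also small: 0.09 × 5 to 0.09 × 10, or 0.45 to 0.9 points, against a prior SD of 5.

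Finally, conservative describes the effect of the omission only. If the true placebo mean were 5 points above 13.7, the 90% rule would be met under no effect in about 15% to 16% of trials with or without the term (simulated with an 8-point gap).

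**Conclusion.** The concern holds, as a refinement that should be made and not as a threat to the conclusion. The primary Bayesian model ignores the randomisation stratum, and no listed Bayesian sensitivity model adds it. Under assumed residual gaps of 5 to 10 points, adding the term would lower the posterior SD by about 1% to 6% when strata are balanced. It would remove a bias of about 0.6 to 1.2 points in the 15/30 against 7/20 example. With no stratum gap there is nothing to gain and almost nothing to lose. The decision at a 13-point effect is practically unaffected. These sizes rest on the assumed gaps and prevalences, 30/20 completers, a total SD of 14, and a true placebo mean equal to the prior mean.

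**What to change.** Add γ(zᵢ − z̄) to the Appendix 4 primary model. Here zᵢ is the anti-TNF stratum as randomised in the IRT, z̄ is its mean over both arms, and γ ~ N(0, 10³). Centring on both arms keeps the placebo mean at the stratum mix for which the N(13.7, 25) prior was derived.

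If the primary model is to stay as it is, list this version as a named Bayesian sensitivity model. That is the minimum, and it leaves the primary analysis in Protocol 9.2.1 unchanged.

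Use the same variable in the sensitivity ANCOVA and MMRM, or state that it is identical to the anti-TNF use covariate named there. Protocol 9.4 refers to exposure with inadequate response, while inclusion criterion 11 also admits subjects who did not tolerate the agent, so the two could be coded differently.

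The cost is one model term and one extra parameter. Because Protocol 9.2.1 names only baseline SDAI, changing the primary model needs a matching protocol edit if the sponsor regards it as a major modification under SAP section 2.
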